### 12.1.1 Sensitivity analyses of the primary endpoint

As a sensitivity analysis for both the primary analysis of ACR30 (+ absence of fever) at Week 2 and the supportive analysis of ACR30 (+ absence of fever) at Week 1 a comparison of treatment groups including the actual response data for patients who have discontinued study drug will be performed using the ACR assessment closest to Week 2 or Week 1 respectively. However, patients with study drug discontinuation due to progressive disease will still be treated as non-responders as in the main analysis. The same exact methods as for the primary analysis will be used.

If the analysis of the primary efficacy endpoint results in a statistically significant outcome a tipping point analysis will be performed. The number of responders that can potentially be observed among patients with a missing ACR30 outcome at Week 2 (e.g. when non-response is assigned in the primary analysis due to discontinuation of study drug) in the anakinra group versus the placebo group will be presented in a basic tipping point display. Pairs of number of responders in the anakinra and placebo group that lead to statistical significance will be marked

and pairs that lead to non-significance will not be marked. The tipping point boundary is the staircase region between marked and unmarked rectangles (Yan et al 2009).

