6.2 Discussion of study design

A randomized placebo controlled double-blind study is the optimal way to document safety and efficacy of an investigational product. In this study the number of patients receiving

placebo has been kept to a minimum, which means that only one third of the patients will be randomized to placebo and two thirds will be randomized to active treatment in two dose levels.

The main comparison will be between anakinra (combined dose groups) and placebo at week 2. In order to be able to evaluate the primary endpoint at week 2, patients that discontinue study drug before week 2 will be encouraged to do a Study Drug Discontinuation visit as well as the Week 2 visit (if the Study Drug Discontinuation visit is performed within 3 days prior to the Week 2 visit, the scheduled Week 2 visit should be omitted). Patients who discontinue study drug will receive standard of care. Options for standard of care will be determined at the discretion of the investigator in dialogue with the patient/caregiver. As patients may already have been administered anakinra in the study this should be taken into consideration when switching to standard of care.

Since IL-1 inhibition has a rapid onset of effect, supported by the published data showing that approximately 90% of patients became afebrile after three days of anakinra treatment and the fact that ACR response rates were similar at day 15 and day 29 in the study with the IL-1 inhibitor canakinumab, it is appropriate to evaluate the primary endpoint after two weeks treatment with anakinra (19, 20, 34). Sustained efficacy of anakinra treatment will be evaluated during the 12 week period for patients who are responders at week 2. In addition, time to study drug discontinuation will be an endpoint for evaluation of efficacy in the study as well as the possibility to taper glucocorticoid treatment.

Trough and repeated PK assessments will be included in this study in order to characterize the pharmacokinetics of anakinra in this patient population.

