8.4.2 Sensitivity analyses

The primary efficacy endpoint and the key secondary endpoints will be analysed using the PP population as described in Section 8.3.4 and 8.3.5.

For patients who discontinue study drug before Week 2, a Study Drug Discontinuation visit should be performed before standard of care treatment is initiated and a Week 2 visit should preferably also be performed (if the Study Drug Discontinuation visit is performed within 3 days prior to the Week 2 visit, the scheduled Week 2 visit should be omitted). As a sensitivity analysis, for both the primary analysis of ACR30 (+ absence of fever) at Week 2 and the supportive analysis of ACR30 (+ absence of fever) at Week 1 a comparison of treatment groups including patients who have discontinued study drug will be performed using the ACR assessment closest to Week 2 or Week 1 respectively. However, study drug discontinuation due to progressive disease will be treated as non-responders.

A tipping point analysis will also be performed for the primary efficacy endpoint. For patients where no plausible assumption can be made depending on the reason for the missing outcome (e.g. patients that discontinue study drug due to lack of efficacy and progressive disease), the number of responders that can potentially be observed among patients with a missing ACR30 outcome at Week 2 in the anakinra group versus the placebo group will be presented in a basic tipping point display. Pairs of number of responders in the anakinra and placebo group that lead to statistical significance will be marked and pairs that lead to non-significance will not be marked. The tipping point boundary is the staircase region between marked and unmarked rectangles (51). This analysis will be repeated allowing the assumptions to vary for all patients with a missing ACR30 outcome at Week 2, except those

patients who have discontinued study drug and fulfilled the escape criteria who will still be treated as non-responders.

9 Data collection, handling and record keeping

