# 4.3 Method of treatment assignment and randomization

The different treatment groups are;

- placebo (corresponding volume of anakinra 2 mg/kg/day [max 100 mg/day]), or
- placebo (corresponding volume of anakinra 4 mg/kg/day [max 200 mg/day]), or
- anakinra 2 mg/kg/day (max 100 mg/day) or
- anakinra 4 mg/kg/day (max 200 mg/day)

The ratio between the treatment groups is 1:1:2:2, i.e. the ratio placebo:anakinra is 1:2.

The randomization numbers are generated in blocks. Each block includes the four treatment groups per the ratio described above. The block size will not be revealed before breaking of the blind.

The randomization is stratified by age at onset of disease (< 16 years,  $\ge$  16 years) and glucocorticoid use at inclusion (yes, no). The original plan was to randomize 81 patients with the requirement to randomize at least a third of the patients with an age at onset of disease < 16 years and a third of the patients with an age at onset  $\ge$  16 years, however this is no longer a requisite due to early stopping of the study. Medidata balance randomization and trial supply system is used for IRS and Biostatistics at DCRI is responsible for generating the randomization scheme, which will link sequential patient randomization numbers to treatment codes.

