# **6** Sample size determination

Assuming the ACR30 response rate with absence of fever at Week 2 is 65 % in patients receiving anakinra and 25 % in placebo patients, 81 evaluable patients (54 anakinra and 27 placebo) would be required to ensure 90 % power in demonstrating that anakinra improves clinical features of Still's disease using a two-sided test at a 5 % significance level. These assumptions are based on the canakinumab and tocilizumab phase 3 clinical studies in SJIA where 65 to 85 % of active patients and 10 to 25 % of placebo patients responded at two weeks,

as well as the Nordstrom study in AOSD where 50 % of anakinra treated patients were in remission after 4 weeks of treatment (Nordstrom et al 2012).

Since recruitment will be stopped before the planned number of evaluable patients have been included, it is anticipated that at least 12 patients will be randomized and included in the analyses.

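### The SAP 12.1.1 sensitivity analysis can count response after standard of care for patients, in either arm, who stopped study drug for lack of efficacy, because only progressive-disease stops are held as failures

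*SAP*

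**What the plan says.** In the primary analysis every patient who stops study drug before Week 2 is a non-responder (SAP 8.2.1 and 12.1).

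SAP 12.1.1 relaxes this with a comparison "including the actual response data for patients who have discontinued study drug will be performed using the ACR assessment closest to Week 2"; the supportive analysis is handled the same way at Week 1. It makes one exception: "patients with study drug discontinuation due to progressive disease will still be treated as non-responders". Protocol 8.4.2 has the same exception: "However, study drug discontinuation due to progressive disease will be treated as non-responders". Neither passage exempts lack of efficacy.

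The visit rules are in SAP 4.1 and Protocol 6.1, 6.3.3 and 6.5.1.9. The Study Drug Discontinuation visit should come before standard of care where possible. A patient who stops before Week 2 should still attend the Week 2 visit on its original date, unless the discontinuation visit fell within the 3 days before it, in which case the Week 2 visit is dropped. Protocol 6.2 adds: "Patients who discontinue study drug will receive standard of care".

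The only other sensitivity analysis of the primary endpoint in the SAP is a tipping point analysis, run only if the primary result is significant (SAP 12.1.1). The protocol's per-protocol population is not among the SAP analysis sets (SAP 7).

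**The concern.** The discontinuation visit is meant to record the patient's state before other treatment begins. When a Week 2 visit is also held, the closest-to-Week-2 rule passes over that record and takes the later one, which can reflect standard of care. A patient for whom the assigned treatment failed can then be scored as a responder in that arm.

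The rule also mixes two approaches. A treatment-policy analysis would use observed data for all stoppers, including those with progressive disease. A composite analysis would count stopping for treatment failure as failure, whether recorded as lack of efficacy or as progressive disease. Elsewhere the documents put the two reasons together: in the time-to-discontinuation endpoint (SAP 3.3.4, Protocol 8.3.6.3) and in the tipping point text of Protocol 8.4.2. No reason is given for separating them here.

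At stake is the reading of the one sensitivity analysis of the primary endpoint that is always run. It could make a sound primary result look fragile or, less probably, lend support to a result that owes something to rescue.

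**Working it through.** **1. The plan's own figure.** SAP 6 assumes "65 % in patients receiving anakinra and 25 % in placebo patients" and states that "81 evaluable patients (54 anakinra and 27 placebo) would be required to ensure 90 % power", "using a two-sided test at a 5 % significance level". Allocation: "The ratio between the treatment groups is 1:1:2:2, i.e. the ratio placebo:anakinra is 1:2".

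- Pooled rate: (27×0.25 + 54×0.65)/81 = 0.517.
- Placebo n without continuity correction: [1.960×√(0.517×0.483×1.5) + 1.282×√(0.25×0.75 + 0.65×0.35/2)]² / 0.40² = 22.6, so 23, total 69.
- With continuity correction: (22.6/4)×[1 + √(1 + 6/(22.6×2×0.40))]² = 26.2, so 27, total 81. This matches the SAP.
- Power of Fisher's exact test, the SAP's test, at 54:27 is 92.0%.

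The planning figure is sound; the point concerns how stoppers are scored.

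**2. Which visit is scored.** Take Week 2 as Day 15.

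- Discontinuation visit on Days 2–11: the Week 2 visit is due, 4–13 days later. If held, it is the closest assessment.
- Discontinuation visit on Days 12–14: the Week 2 visit is omitted and the discontinuation visit is scored.

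If stops were spread evenly over Days 2–14 and all due visits were held, 10/13 = 77% would be scored at Week 2. Both conditions are assumptions.

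**3. Direction.** Let f be the share of non-responders who stop for lack of efficacy before Week 2, s the share of those scored after rescue, and r the response rate after rescue. Scored rates are:

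- anakinra: 0.65 + 0.35×f×s×r
- placebo: 0.25 + 0.75×f×s×r

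With common f, s and r the difference is 0.40×(1 − f×s×r), so it can only shrink. If f differs by arm, with s and r common, it shrinks unless the anakinra share exceeds the placebo share by a factor of more than 0.75/0.35 = 2.1.

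**4. Size.** The documents give none of f, s or r. All values below are assumptions, applied equally to both arms.

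| f | s | r | Anakinra v placebo | Difference (points) | Fisher power 54:27 | Fisher power 8:4 |
|---|---|---|---|---|---|---|
| 0 | – | – | 65.0% v 25.0% | 40.0 | 92.0% | 6.7% |
| 0.10 | 0.77 | 0.40 | 66.1% v 27.3% | 38.8 | 89.9% | 6.7% |
| 0.25 | 0.77 | 0.65 | 69.4% v 34.4% | 35.0 | 82.5% | 6.6% |
| 0.50 | 1.00 | 0.40 | 72.0% v 40.0% | 32.0 | 75.8% | 6.4% |
| 0.50 | 1.00 | 0.65 | 76.4% v 49.4% | 27.0 | 63.0% | 5.6% |

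With different shares by arm (placebo 30–50%, anakinra 10–30%; r 0.30–0.65; s 0.77–1.00), 16 combinations gave differences of about 18–37 points and Fisher power of about 29–87% at 54:27. All 16 shrank.

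**5. The trial now expected.** SAP 4.2 and 6 expect at least 12 patients at 2:1, so about 8 v 4. Two-sided Fisher p-values from table counts:

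- 7/8 v 0/4: 8/792 = 0.010. Rescoring one placebo patient gives 7/8 v 1/4: 33/495 = 0.067.
- 6/8 v 0/4: 56/924 = 0.061. Rescoring one anakinra patient gives 7/8 v 0/4: 0.010.

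One rescored patient can therefore cross 0.05 in either direction.

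**The case against.** Much of the case on the other side stands.

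- **The primary analysis is untouched.** The sensitivity analysis exists to relax its rule, and scoring lack of efficacy as failure brings the two closer together. That is a real cost of the fix.
- **A fragile-looking result will not stand alone.** If the primary result is significant, the tipping point analysis is also run, and it covers patients set to non-response because they discontinued. This does not help in the 6/8 v 0/4 case, where the primary result is not significant and no tipping point analysis follows.
- **The exposure is limited.** The 3-day rule and missed Week 2 visits lead back to the earlier visit; Protocol 6.2 only encourages attendance. The endpoint also requires 7 days free of disease fever, so a patient who stops around Day 8 or later with continuing fever cannot become a responder by Day 15.
- **Individual cases will be visible.** The by-visit listing (SAP 12.1) and swimmer plots (SAP 12.4.1 and 12.4.4) will let a reader trace them in so small a trial.
- **The rule is prespecified**, and treating stopping reasons differently is not in itself an error. What is missing is a statement of the question this mixture answers.

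A reader might infer more than the documents support. One inference is that the rule favours anakinra by crediting it with rescue. It applies to both arms, and the likelier effect is dilution. Another is that the scored visit usually follows standard of care. The schedule makes that plausible, but no start day or frequency is given. A third is that power falls from 92% to 63%. That figure needs half of all non-responders to stop early for lack of efficacy, every one of them scored after rescue, and 54:27 patients.

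**Conclusion.** The point holds in a limited form. As written, the analysis can count response after standard of care for a lack-of-efficacy stop, in either arm, while progressive disease stays a failure, so it has no single clear estimand.

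Dilution is the likely direction, provided the placebo arm has more non-responders to rescue, as the planning rates imply. The size cannot be fixed from the documents. Under mild assumptions the 40-point planning difference falls to 35–39 points; under the heaviest tried, to about 18. The corresponding losses of power at 54:27 do not describe the trial now expected: at 8:4, power is about 6–7% with or without the rule in the scenarios tabulated. What matters at that size is that a single rescored patient can change the result.

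This is a low-cost improvement to a supportive analysis. It does not threaten the primary result.

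**What to change.** In SAP 12.1.1:

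1. Score study drug discontinuation for lack of efficacy as non-response, like progressive disease, and use observed data only for stops for other reasons.
2. If a treatment-policy view is wanted, add it as a separate, labelled analysis using observed Week 2 data for all stoppers, including those with progressive disease.
3. If stops for other reasons are to be scored at a visit before standard of care, say which fever window applies. Protocol 6.5.1.9 records only the preceding 24 hours when the discontinuation visit falls before Week 1, so the 7-day condition cannot be assessed as defined. State that the window recorded at that visit is used.

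The cost is a few lines of SAP text, with one extra table if both versions are kept. The revised analysis departs less from the primary analysis and so tests less. A pre-standard-of-care visit may also lie several days before Week 2.

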### 12.2 Secondary endpoints supporting the primary objective

For ACR30, ACR50, ACR70 and ACR90, with absence of fever in the preceding 24 hours at Week 1 and ACR50, ACR70 and ACR90, with absence of fever in the preceding 7 days, at Week 2, the proportion of patients with a response in each treatment group, along with 95 % exact confidence intervals and exact tests of the difference in response between treatment groups, will be presented. The same exact methods as for the primary endpoint will be used. Patients who have discontinued study drug prior to the relevant week of the analysis (Week 1 or Week 2) will be treated as non-responders in the analyses.

The response in the individual components of ACR30, ACR50, ACR70 and ACR90, respectively, at Week 1 and Week 2 will be analyzed in the same way as the primary endpoint using exact statistical methods. The proportion of patients with a response in each group, and exact confidence intervals of the difference will be presented. Patients who have discontinued study drug prior to Week 1 will be treated as non-responders in the analyses of the individual components of ACR at Week 1 and patients who have discontinued study drug prior to Week 2 will be treated as non-responders in the analyses of the individual components of ACR at Week 2.

The numbers of patients with response/no response in the individual components of ACR at Week 1 and Week 2 will also be presented in bar charts.

The absence of fever at Week 2 will be analyzed in the same way as the primary endpoint using exact statistical methods. Patients who have discontinued study drug prior to Week 2 will be treated as having a presence of fever in the analysis.

### 12.3 Key secondary efficacy endpoints

The absence of fever at Week 1 will be analyzed in the same way as the primary endpoint using exact statistical methods.

For each of the three continuous endpoints; change at Week 1 in CRP, in physician's global assessment of disease activity and in patient/parent global assessment of overall well-being, descriptive statistics for each treatment group will be calculated. For the comparison between anakinra and placebo, exact rank tests based on Wilcoxon scores will be used. The exact 95% confidence intervals based on the Wilcoxon rank statistic for the Hodges-Lehmann estimate of the treatment difference, will be calculated.

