8.3.5 Analysis related to key secondary objective

To evaluate the key secondary objective, the following endpoints will be analyzed:

- Absence of fever during the 24 hours preceding Week 1.

- Change from baseline in physician global assessment of disease activity (VAS) at Week 1.
- Change from baseline in patient/parent global assessment of overall well-being (VAS) at Week 1.
- Change from baseline in CRP at Week 1.

The absence of fever at Week 1 will be analyzed using a logistic regression model with treatment, age at onset of disease (< 16 years, ≥ 16 years) and glucocorticoid use (yes, no) as explanatory variables. Patients who discontinued study drug prior to Week 1 will be treated as having a presence of fever in the analysis. The estimated probability of absence of fever in each treatment group, the estimated odds ratio of anakinra to placebo, the corresponding 95 % confidence interval and the p-value from the model will be presented.

The three continuous endpoints; change in CRP, change in physician's global assessment of disease activity and change in patient/parent global assessment of overall well-being, will be analyzed using a mixed model repeated measurement with the measurements on the individual timepoints (i.e. Baseline and Week 1 or if the Week 1 visit is not performed due to Study drug discontinuation before Week 1 the Study drug Discontinuation visit will be used) as responses and with treatment, age at onset of disease (< 16 years, ≥ 16 years) and glucocorticoid use (yes, no), visit and treatment-visit interaction as fixed effects. For the comparison between anakinra (combined dose groups) and placebo for each endpoint, the estimated difference, the associated 95 % confidence interval and the p-value from the model will be presented.

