#### 3.3.3 Key secondary efficacy endpoints

The key secondary efficacy endpoints are:

- Absence of fever during the 24 hours preceding Week 1.
- Change from baseline in physician global assessment of disease activity (VAS) at Week
- Change from baseline in patient/parent global assessment of overall well-being (VAS) at Week 1.
- Change from baseline in CRP at Week 1.

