# 4.2 Selection of study population

A total of 81 patients was originally planned to be randomized, but fewer patients are expected since recruitment will be stopped earlier. At least 12 patients are expected to be randomized, with a 2:1 allocation (anakinra:placebo).

For inclusion into the study, a patient should have active Still's disease, diagnosed not more than 6 months prior to randomization. Diagnosis of Still's disease:

- a) If < 16 years of age at disease onset, according to adapted ILAR criteria i.e., CARRAcriteria for SJIA.
- b) If  $\geq 16$  years of age at disease onset, according to Yamaguchi criteria.

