# 8 General issues for statistical analysis

The comparison of interest is between anakinra (2 mg/kg and 4 mg/kg combined) and placebo. Due to the small number of patients in the individual dose groups of anakinra, summary tables (except for the drug exposure summary) will not provide results by individual dose groups. Likewise, the randomization was stratified by age at onset of disease (< 16 years,  $\geq$  16 years) and glucocorticoid use (yes, no), but due to the very small number of patients for levels of the stratification factors within each treatment group, descriptive statistics and statistical analyses will generally not be performed by stratification factors. For primary and key secondary efficacy endpoints, dose-level information and stratification allocation will be included in a patient listing.

All statistical tests will be two-sided and performed using a 5 % significance level, if not stated otherwise. Results will be presented as the estimated value for each treatment group, anakinra and placebo, the estimated difference between groups, the associated 95 % two-sided confidence interval and p-value. P-values from statistical analyses will be presented to three decimal places with values below 0.001 displayed as <0.001 and 95 % confidence intervals will be presented to one more decimal place than the raw data.

Continuous data will be summarized using descriptive statistics: n, mean, SD, median, minimum and maximum, unless otherwise indicated. Minimum and maximum will be presented to the same number of decimal places as the raw data and mean, SD, and median will be presented to one more decimal place than the raw data.

Categorical data will be summarized using counts and percentages. Percentages will be suppressed when the count is zero, however the category will still be displayed. The denominator for all percentages will be the number of patients within the treatment group for the population of interest, unless otherwise indicated. Percentages will be presented to one decimal place.

Statistical analyses will be performed using SAS software Version 9.4 (SAS Institute Inc, Cary, North Carolina, United States).

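### SAP 12.3 compares Week 1 change in the two global VAS scores without using the baseline score, so at about 8 versus 4 patients a chance baseline imbalance carries into the estimate and interval

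*SAP*

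**What the plan says.** SAP 3.3.3 defines the endpoints as absolute change, for example "Change from baseline in patient/parent global assessment of overall well-being (VAS) at" Week 1. SAP 12.3 covers three continuous endpoints in one sentence: "change at Week 1 in CRP, in physician's global assessment of disease activity and in patient/parent global assessment of overall well-being". The method is "For the comparison between anakinra and placebo, exact rank tests based on Wilcoxon scores will be used", and for estimation "The exact 95% confidence intervals based on the Wilcoxon rank statistic for the Hodges-Lehmann estimate of the treatment difference, will be calculated". No covariate is named. SAP 8 adds that "descriptive statistics and statistical analyses will generally not be performed by stratification factors". The sensitivity analyses in SAP 12.1.1 concern ACR30 only.

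The model in Protocol 8.3.5 took baseline and Week 1 as two responses, with treatment, the two stratification factors, "visit and treatment-visit interaction as fixed effects". Baseline was an outcome in that model, not a covariate.

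SAP 8.4 tests the key secondary endpoints only if the primary null hypothesis is rejected, and calls all secondary testing exploratory. SAP 4.2 expects at least 12 randomized patients at 2:1, which is about 8 anakinra and 4 placebo.

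**The concern.** A change score subtracts the whole baseline value, which is the best correction only if the Week 1 score follows baseline with slope 1. With equal variances at the two times the slope is ρ. Below 1, change over-corrects: the arm that starts worse appears to improve more, whatever the drug does. In a large trial this averages out. With 4 placebo patients a sizeable chance imbalance is to be expected, and the planned contrast passes part of it on as an apparent treatment difference. The baseline scores that would allow a correction are scheduled for every patient on Day 1.

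The two VAS scores are two of the four key secondary endpoints. Their estimates and intervals are what a reader will look at if the primary test is not significant.

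**Working it through.** **Inputs from the documents.** Two-sided 5% level (SAP 8). At least 12 patients at 2:1 (SAP 4.2), taken as 8 and 4. VAS 0–100 mm (Protocol 6.5.4.1.1). Response rates 65% and 25% (SAP 6).

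**Assumptions, because the documents give no figure.** SD 20 mm at both times, a true difference of 25 or 30 mm, and ρ from 0 to 0.9.

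**The plan's own figure.** SAP 6 gives 81 patients (54 + 27) for 90% power at 65% versus 25%. The two-proportion formula at 2:1 with continuity correction gives 27 + 54 = 81, which matches. Without the correction it gives 23 + 46 = 69. No such figure is given for the VAS endpoints.

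**How often the gate opens at 8 versus 4.** Fisher's test favours anakinra significantly only for 7/8 v 0/4, 8/8 v 0/4 and 8/8 v 1/4.
- Anakinra at 65%: P(7) = 8 × 0.65⁷ × 0.35 = 0.137; P(8) = 0.65⁸ = 0.032.
- Placebo at 25%: P(0) = 0.75⁴ = 0.316; P(1) = 4 × 0.25 × 0.75³ = 0.422.
- Power = 0.137 × 0.316 + 0.032 × (0.316 + 0.422) = 0.067, about 7%.

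At 85% versus 10% it is 51%.

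**Baseline imbalance.** SE of the baseline difference = 20 × √(1/8 + 1/4) = 12.2 mm. Change has slope −(1 − ρ) on baseline, so a one-SE imbalance shifts the contrast by (1 − ρ) × 12.2 mm. An imbalance beyond one SE in either direction occurs in about one trial in three.

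**Power and interval width.** These come from simulated trials with all 495 allocations enumerated. The planned exact Wilcoxon test on change is compared with the same test on residuals from regressing the Week 1 score on baseline over all patients, ignoring treatment. Power is for 25 mm. Width is the mean for 30 mm.

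| ρ | Shift per one-SE imbalance (mm) | Power, change → adjusted | 95% interval width, change → adjusted (mm) |
|---|---|---|---|
| 0 | 12.2 | 24% → 38% | – |
| 0.3 | 8.6 | 31% → 41% | 66 → 58 |
| 0.5 | 6.1 | 41% → 47% | 54 → 50 |
| 0.7 | 3.7 | 60% → 61% | 42 → 43 |
| 0.8 | 2.4 | 79% → 75% | 32 → 37 |
| 0.9 | 1.2 | 97% → 93% | – |

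Overall type I error is about 5% for both tests. The widths rest on 200 trials per row, and the adjusted interval is sometimes much wider than its average. It was wider than the planned one in 23%, 35% and 40% of trials at ρ 0.3, 0.5 and 0.7. The 0.5 and 0.7 rows are best read as near break-even.

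**Check on the break-even.** The large-sample variance ratio of adjusted to change is (1 − ρ²) / [2(1 − ρ)] = (1 + ρ)/2. Estimating a slope from 12 patients multiplies this by about 9/8. The product equals 1 at ρ = 16/9 − 1 = 0.78 for a linear model. The residual rank test breaks even slightly earlier, near 0.7.

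**Shape of the effect.** With a bounded VAS (baseline mean 60 mm) and a drug that halves the Week 1 score, the gain is larger and lasts longer: 51% → 71% at ρ 0.3, 79% → 86% at 0.7, 98% → 96% at 0.9.

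**Results given the imbalance seen.** With a 30 mm effect and ρ 0.5, the planned test has 80% power when anakinra starts more than one SE worse and 29% when placebo does. The adjusted test has 46% and 45%. With no effect, the planned test rejects in about 8% of trials with such an imbalance, and the adjusted test in about 3%.

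**The case against.** The case for leaving SAP 12.3 alone is substantial.

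- **The test is valid.** It holds its level over randomization, and chance imbalance is already reflected in the width of the interval. A reader might infer an inflated false-positive rate, but overall type I error is about 5%. The 8% above applies only given a marked imbalance. At ρ 0.3 the 9 mm shift is also small beside a 66 mm interval. All this stands.
- **The tests are gated and exploratory.** A reader might conclude that the SAP wastes material power on confirmatory endpoints. SAP 8.4 does not support that, since at the design rates the gate opens in about 7% of trials. This stands for the p-values. It does not cover the estimate and interval, which SAP 12.3 calculates without condition.
- **The SAP did not drop an adjustment.** The move away from the protocol's mixed model might be read as removing a baseline correction. With complete data, that model's contrast was also a difference in mean change, so this is not a new departure.
- **Other baseline-relative views exist.** SAP 12.2 analyses each ACR component, including both VAS scores, as 30/50/70/90% improvement at Week 1. SAP 12.4.2 plots individual values and percentage change. With about 12 patients an imbalance would be visible. This reduces the harm, but none of it gives an adjusted estimate.
- **ρ is unknown, and adjustment can lose.** This stands. Any statement of gain has to be a range that includes a loss.

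**Conclusion.** The point holds as one about estimation. SAP 12.3 leaves the baseline score out of the comparison for both VAS endpoints, and CRP shares the sentence and the method. At 8 versus 4 with SD 20 mm, each one-SE baseline imbalance (12 mm) moves the treatment contrast by about 9, 6 or 4 mm at ρ 0.3, 0.5 or 0.7. The direction holds for any ρ below 1 with equal variances. The size scales with the assumed SD.

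The power argument is secondary and conditional. For an additive 25 mm effect, adjustment gains 14 points at ρ 0, 10 at 0.3 and 6 at 0.5, nothing at 0.7, and loses about 4 at 0.8–0.9. Mean interval width follows the same pattern. The documents do not support calling the planned test invalid, or claiming that adjustment is better whatever the correlation. The practical weight is modest, but the change is cheap and would be post hoc after unblinding.

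**What to change.** Before database lock, add to SAP 12.3 a prespecified baseline-adjusted exact analysis of the two VAS endpoints:

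1. Regress the Week 1 score on the baseline score over all patients, ignoring treatment.
2. Apply the exact Wilcoxon test to the residuals. With no treatment effect, the residuals do not depend on assignment, so the permutation argument is the same as for the planned test.
3. Obtain the 95% interval by inversion: subtract each candidate difference from the anakinra Week 1 scores, repeat steps 1 and 2, and keep the values not rejected.

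Report it alongside the planned change-score analysis at minimum, and say in advance which of the two leads. State whether CRP is handled the same way, so that one paragraph does not hold two methods by default.

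Cost: a few lines of SAP text, some custom code for the inversion, a less familiar output, and a small loss of precision if the correlation is above about 0.7. No new data are needed.
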